6.3.1.2 Full screening failure

A patient who passes the prescreening, including the mesothelin overexpression testing, but for any other reason (e.g., failure to satisfy the remaining selection criteria) terminates the study before enrollment is regarded as a “full screening failure”. See Section 11.1 for data to be collected for screening failures.

Re-starting the defined set of screening procedures to enable the “screening failure” patient’s participation at a later time point is not allowed – with the following exceptions:

- The patient had successfully passed the screening procedures, but could not start subsequent treatment on schedule.
- Initial screening occurred too early to complete the required washout period after prior therapy.
- The in- / exclusion criteria preventing the patient’s initial attempt to participate have been changed (via protocol amendment).
- Equivocal screening results require further testing for clarification even if, for logistical reasons, the further testing cannot be performed within the allocated time window (e.g. equivocal laboratory creatinine clearance requiring formal creatinine clearance measurement).
- Resolution of toxicity, now meeting all criteria

In any case, the investigator has to ensure that the repeated screening procedures do not expose the patient to an unjustifiable health risk. Also, for re-screening, the patient has to resign the main consent document (for the full study), even if it was not changed after the patient’s previous screening.

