6.3.2 Withdrawal criteria

All patients who enter the study should complete all phases of the study unless they are screen failures or meet the criteria for withdrawal. Phases of the study include:

1. Prescreening
2. Full screening
3. Registration
4. Treatment
5. Safety follow-up
6. Active follow-up
7. Long-term follow-up

Study treatment discontinuation (i.e., discontinuation during the treatment period) does not constitute withdrawal from the study.

Every effort should be made to retain patients who discontinue the treatment period for any reason. These patients are to be encouraged to remain on the study for follow-up of primary, secondary and other objectives (i.e., continue in the safety follow-up, active follow-up and/or long-term follow-up periods).

Patients are expected to participate in the follow-up unless they explicitly object. Withdrawal of consent to treatment should be documented in the patient's medical record. If the patient does not wish to be followed up further, this additional consent withdrawal for follow up would have to be documented, too.

Withdrawal from study treatment, active follow-up and long-term follow-up

Patients withdrawn from **the study treatment** phase of the study should be followed for primary, secondary and other objectives (i.e. continue in the safety follow-up, active followup and/or long-term follow-up periods) (see Figure 2-1 for withdrawal criteria).

[figure not shown]
Figure 2-1 Withdrawal criteria

PATIENTS MUST BE WITHDRAWN FROM THE STUDY TREATMENT IF ANY OF THE FOLLOWING OCCURS:

- At their own request or at the request of their legally acceptable representative. At any time during the study and without giving reasons, a patient may decline to participate further. The patient will not suffer any disadvantage as a result.
- If, in the investigator's opinion, continuation of the study treatment would be harmful to the patient's well-being.
- At the specific request of the sponsor and in liaison with the investigator (e.g. obvious non-compliance, safety concerns).
- Confirmed radiological PD as per RECIST criteria.
- Clinical progression as assessed by investigator. Occurrence of unacceptable toxicity to anetumab ravtansine (see also Section 7.3.2).
- CTCAE Grade 4 hypersensitivity and acute infusion reaction.
- An adverse reaction deemed sufficiently serious to warrant discontinuation of treatment by the investigator or his designated associate(s).
- Development of a secondary malignancy.

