- Patient starts treatment with any other anti-cancer therapy or any other prohibited medication as per Section 8.1.
- Positive serum β -HCG test consistent with pregnancy. Pregnancy should be reported along the same timelines as an SAE.
- Use of illicit drugs or other substances that may, in the opinion of the investigator or his designated associate(s), have a reasonable chance of contributing to toxicity or otherwise confound the results.
- Development of any intercurrent illness or situation which may, in the judgment of the investigator, affect assessments of clinical status and study endpoints to a relevant degree.
- Lost to follow-up.
- Death.

Patients must be withdrawn from **treatment with anetumab ravtansine** if any of the following occurs:

- CTCAE Grade 4 non-hematological AE and Bayer Grade 4 corneal toxicity (see Table 2-6) (except at the investigator's discretion in case of certain Grade 4 abnormality of laboratory assessments, such as abnormal laboratory assessments without corresponding clinical symptoms, or abnormal laboratory assessments that can be easily clinically managed).
- If any type of TEAE requiring dose modification does not resolve to Grade ≤ 1 (or Hb ≥ 8 g/dL in case of anemia) within 6 weeks after the last dose of anetumab ravtansine.
- Delay in anetumab ravtansine administration of 3 weeks (max. 6 weeks between 2 infusions of study drug).
- TEAE requiring dose reduction when already at the 4.5 mg/kg Q3W dose level (minimum dose).
- More than 2 dose reductions required due to a TEAE.

AE = Adverse event; β -HCG = β subunit of human chorionic gonadotropin; CTCAE = Common Terminology Criteria for Adverse Events; Hb = Hemoglobin; RECIST = Response Evaluation Criteria in Solid Tumors; PD = Progressive disease; Q3W = Every 3 weeks; SAE = Serious adverse event; TEAE = Treatment-emergent adverse event

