7.3.2 Dose modification

The NCI-CTCAE v4.03 will be used to assess toxicities; in addition, a Bayer grading system (see **Table 2-6** and **Table 2-7**) will be used to assess corneal toxicity.

TEAE requiring dose modification (temporary treatment interruption, dose reduction, or permanent discontinuation of treatment) will be defined as any of the events described below that is possibly, probably, or definitely related to anetumab ravtansine and occurs anytime during the study (not only in Cycle 1).

The dose reduction levels of anetumab ravtansine will follow pre-defined dose levels shown in **Table 2-2**.

Dose level 1 (starting dose):	6.5 mg/kg Q3W
Dose level -1:	5.5 mg/kg Q3W
Dose level -2:	4.5 mg/kg Q3W

Q3W = Every 3 weeks

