7.3.2.1 Hematological toxicities

Dose modifications for hematological toxicity

- If treatment modification is required due to a hematological TEAE, and the continuation of treatment is appropriate, the anetumab ravtansine dose will be adjusted as described in **Table 2-3** and **Table 2-4** below.
- G-CSF and other hematopoietic growth factors may be used during the study in the management of acute toxicity such as febrile neutropenia when clinically indicated per ASCO Recommendations for Therapeutic Use of CSF (26) or at the discretion of the investigator; however, they may not be substituted for a required dose reduction.
- Blood transfusions and therapy with IV or subcutaneous erythropoietin-stimulating agents (epoetin alpha, darbepoetin alpha) are allowed per institution guidelines but may not be used as substitute for a required dose reduction (see also **Table 2-8**).
- Platelet transfusion may be used during the study in the management of acute toxicity such as hemorrhage or bleeding events, however they may not be used as substitute for a required dose reduction.

Table 2-3: Dose adjustments in response to neutrophil and platelet nadir ^a counts of the previous cycle

Absolute neutrophil nadir count of the previous cycle (/mm³)		Platelet nadir count of the previous cycle (/mm³)	Anetumab ravtansine dose adjustment ^b
≥ 500 or < 500 for < 7 days	and	≥ 25,000	No change
< 500 for ≥ 7 days	and/	< 25,000 regardless of the presence of active bleeding (or ≥ 25,000 with clinically significant bleeding, i.e. bleeding requiring platelet transfusion)	Decrease 1 dose level ^b
Febrile neutropenia ^c	and/	< 25,000 regardless of the presence of active bleeding (or ≥ 25,000 with clinically significant bleeding, i.e. bleeding requiring platelet transfusion)	Decrease 1 dose level ^b

ANC = Absolute neutrophil count; C = Cycle; CBC = Complete blood count; D = Day; Q3W = Every 3 weeks

- a Site visits and blood test for CBC (and biochemistry) on D8 and D15 will be performed on C1, C2 and C3 only. From Cycle 4 onwards, visits and procedures on D8 and D15 are no longer required.
- b Dose reduction by 1 dose level translates to a change from 6.5 mg/kg Q3W to 5.5 mg/kg Q3W, or from 5.5 mg/kg Q3W to 4.5 mg/kg Q3W. Not more than 2 dose reductions from the starting dose level are permitted.

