Corneal Morphology	No pathologic changes	Any stage of superficial punctate keratitis ^a	Epithelial opacities Micro-Cysts Micro-deposits Corneal erosion Corneal erosion Stromal opacity: non-central	Corneal ulcer without risk of acute rupture Stromal opacity: central	Corneal ulcer more severe than Grade 3
	Grade 0	Grade 1	Grade 2	Grade 3	Grade 4
Eye Treatment ^b	Ocular lubricants at the discretion of investigator, in consult with ophthalmologist	Ocular lubricants; add topical steroids if superficial punctate keratitis shows treatment-emergent progression by ≥ 2 SPK Grades	Intensive Treatment with ocular lubricants enhanced with ointments; topical steroids; therapeutic contact lens may be considered at the discretion of investigator in consult with ophthalmologist	Intensive therapy with ointments; topical steroids; therapeutic contact lens or occlusion recommended at the discretion of investigator in consult with ophthalmologist	Intensive therapy with lubricants, ointments, topical steroids and antibiotics as needed; occlusion or therapeutic contact lens recommended; amniotic membrane transplant and other locally approved therapies to be considered at the discretion of investigator in consult with ophthalmologist

Clinical Study Protocol

18-December-2017

BAY 94-9343 (Anetumab in Pancreatic Cancer)
Version 2.0

Page: 33 of 77

	Grade 0	Grade 1	Grade 2	Grade 3	Grade 4
Anetumab ravnansine^c	No change	No change	Keep treatment dose level and schedule if the ophthalmological exam can be performed as needed; otherwise consider dose reduction by -1 dose level without dose schedule change at the discretion of investigator in consult with ophthalmologist	1) Decrease dose to -1 dose level (or -2 dose level if event does not resolve to Grade ≤ 2 at the -1 dose level within 3 weeks) 2) Re-start at the original dose level if the first Grade 3 event resolves to Grade ≤ 2 within 3 weeks and does not recur 3) If not resolved within 3 weeks continue at reduced -2 dose level (or -3 dose level)	Discontinue treatment

SPK = Superficial punctate keratitis a Oxford Schema must be used for grading SPK from stage 0 to VI.

- b Other remedial therapies for corneal epitheliopathy may be added or substituted at investigator's discretion or according to the institutional standards.
- c Treatment decisions are based on corneal morphology changes only, not on visual acuity changes.

Clinical Study Protocol

18-December-2017

BAY 94-9343 (Anetumab in Pancreatic Cancer)
Version 2.0

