7.3.2.5 Permanent discontinuation of anetumab ravtansine due to TEAEs

See Section 6.3.1.2 for withdrawal criteria.

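### Three safety rules contradict themselves as written: an undefined -3 dose level (Table 2-6), five drug entries both permitted and prohibited (Tables 2-9 and 2-8), and two hemoglobin limits for stopping (Figure 2-1 and Table 2-4)

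*Combined protocol and SAP*

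**What the plan says.** **Corneal dose reduction.** In Table 2-6 (Section 7.3.2.3), the third item under Grade 3 reads "If not resolved within 3 weeks continue at reduced -2 dose level (or -3 dose level". Section 7.3.2 states: "The dose reduction levels of anetumab ravtansine will follow pre-defined dose levels shown in" Table 2-2. That table lists 6.5 mg/kg (start), 5.5 mg/kg (-1) and 4.5 mg/kg (-2), every 3 weeks. Table 2-3 footnote b adds "Not more than 2 dose reductions from the starting dose level are permitted", and footnote c of Tables 2-4 and 2-5 repeats it. The reasons for withdrawal from the drug in Figure 2-1 include "TEAE requiring dose reduction when already at the 4.5 mg/kg Q3W dose level (minimum dose" and "More than 2 dose reductions required due to a TEAE". For permanent discontinuation, Section 7.3.2.5 says only "See Section 6.3.1.2 for withdrawal criteria". The section it names is headed "6.3.1.2 Full screening failure"; the rules themselves stand under "6.3.2 Withdrawal criteria".

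**Concomitant drugs.** Table 2-8 prohibits the strong CYP3A4 inhibitors listed in Appendix 16.5 from 2 weeks before treatment until the safety follow-up visit, and notes that DM4 is a CYP3A4 substrate. Table 2-9 permits strong P-gp inhibitors for all patients, with caution and monitoring, and gives a list of examples. Figure 2-1 requires withdrawal from study treatment if a medication prohibited under Section 8.1 is started.

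**Anemia.** Figure 2-1 requires withdrawal if anemia has not recovered to at least Hb 8 g/dL within 6 weeks of the last dose. Table 2-4 footnote b sets the same 6-week rule at Hb 9 g/dL. The hemoglobin row that carries this footnote delays dosing only until Hb 8, and the inclusion limit in Section 6.1.2 is also Hb 8.

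**The concern.** These are mandatory stop and prohibition rules, and each can be read in two ways for the same patient. Table 2-6 tells the investigator to continue at a level with no mg/kg value, where Figure 2-1 says to withdraw. Corneal disorders are this drug's adverse event of special interest (Section 9.5.1.6), so Table 2-6 is a table that sites will use. A patient given clarithromycin is to be monitored under Table 2-9 but withdrawn under Table 2-8 with Figure 2-1. A patient whose hemoglobin recovers to 8.5 g/dL stays on treatment under Figure 2-1 and comes off it under footnote b. What is at stake is consistent and safe handling of individual patients, not the statistical design.

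**Working it through.** There is no planned figure to reproduce. The check sets the rules side by side.

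**1. Dose levels**

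- Levels defined in Table 2-2: 6.5, 5.5 and 4.5 mg/kg. Steps below the start: 3 - 1 = 2, namely -1 and -2.
- Permitted reductions (Table 2-3 footnote b): 2. This agrees with Table 2-2.
- Lowest level named in Table 2-6: -3. That needs a third reduction, which is beyond the cap and has no dose attached.
- Figure 2-1 for a patient who needs a reduction at 4.5 mg/kg: withdraw from the drug.
- The stop rule therefore exists, but Table 2-6 contradicts it, and Section 7.3.2.5 sends the reader to the screening-failure section to find it.

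**2. Drug lists**

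- Table 2-9 P-gp list: 19 entries, with lopinavir and ritonavir counted as one.
- Appendix 16.5 strong CYP3A4 inhibitors: 17 entries.
- Entries in both, matched by name: clarithromycin, conivaptan, itraconazole, ketoconazole, lopinavir/ritonavir. That is 5 of 19.
- Table 2-8 does not name these five; the ban reaches them through its reference to Appendix 16.5.
- No sentence in Section 8.1 says which table prevails.

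**3. Hemoglobin at 6 weeks after the last dose**

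| Recovered Hb (g/dL) | Figure 2-1 | Table 2-4 row | Table 2-4 footnote b |
|---|---|---|---|
| below 8 | withdraw | keep delaying | discontinue |
| 8 to below 9 | continue | may resume | discontinue |
| 9 or above | continue | may resume | continue |

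The rules disagree only in the middle band. There the footnote conflicts both with Figure 2-1 and with its own row.

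**4. How often**

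The documents give no Grade 3 corneal rate, no anemia rate and no rate of use of the five drugs, so the number of affected patients cannot be computed. The nearest figure is in Section 3.1. In the earlier 6.5 mg/kg expansion cohort (ovarian cancer and mesothelioma), 16 of 32 patients had a first reduction, and 4 of those 16 (25%) went on to 4.5 mg/kg. That is 4/32 = 12.5% reaching the lowest level for any cause, or 0.125 x 30 = 3.75 patients if the same rate held in 30. It does not count patients who meet the -3 conflict, because that also needs a Grade 3 corneal event that calls for a reduction below 4.5 mg/kg.

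**The case against.** The strongest reply is that the surrounding text already contains each error.

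- **The -3 level.** It cannot be given because it has no dose, the two-reduction cap is stated in three tables, and Figure 2-1 is explicit. This is largely right. A reader might infer that patients could be treated at -3, or that the protocol has no stop rule. The documents support neither. The realistic result is a site query or a late stop. What stands is that the table says to continue where the rule says to withdraw, and the pointer to the rule is wrong.
- **The drug lists.** The ban appears in Table 2-8, in exclusion criterion 22 and in Figure 2-1, and a site that follows Table 2-8 breaks nothing. That is true, but Table 2-9 names the same drugs as permitted and reads as complete, so a site using it has no reason to ask.
- **Hemoglobin.** Under its own row, Table 2-4 lets a patient at 8 to 9 g/dL be re-dosed, after which the 6 weeks run from the new dose. Discontinuation then follows only if the footnote is applied literally. This narrows the consequence. It leaves a footnote that contradicts its own row.

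The Table 2-6 pages carry a Version 2.0 header, but they sit in the body of the current protocol, not in its amendment log, so the table is in force.

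**Conclusion.** The three conflicts are real and should be corrected, because each lets a stated safety rule be read in opposite ways. Few patients are likely to be affected. That is a judgment, since the documents give no rates for the events that matter. Sample size, error rates and response rate are unaffected: the design's limits are response counts at 20 and 30 patients and do not use these rules.

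Two further readings are tempting, and the text does not support them.

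- A reader might infer that Table 2-6 item 2 (return to the original dose after a first Grade 3 corneal event) breaks the ban on re-escalation in Section 7.3.2.2. The dose-modification paragraph there sets corneal toxicity aside, and an event that clears before the next infusion involves no reduced dose. A contradiction is not established.
- A reader might infer that Table 2-5 must be changed to re-start only at Grade 1 or below. Footnote b of that table and the matching rule in Figure 2-1 are 6-week discontinuation limits, not re-start grades. The one competing re-start rule is in Section 7.3.2.4, which requires a grade below 2 where Table 2-5 accepts Grade 2. Table 2-5 also treats Grade 1 to 2 events on time, and Figure 2-1 withdraws patients after a 3-week delay, so a stricter rule could take patients off treatment. This is a query for the sponsor, not an error with an obvious repair.

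**What to change.** 1. **Table 2-6, Grade 3, item 3:** delete the -3 option and add that treatment is discontinued if a further reduction is needed at 4.5 mg/kg. In Section 7.3.2.5, change the cross-reference to Section 6.3.2, Figure 2-1.
2. **Table 2-9, P-gp row:** exclude strong CYP3A4 inhibitors listed in Appendix 16.5 and state that the Table 2-8 prohibition prevails. Removing the five names alone is not enough, because the list only gives examples and the class would stay permitted.
3. **Anemia limit:** use one value in Figure 2-1 and Table 2-4 footnote b. Hb 8 g/dL is the value the rest of the text supports. It is the less conservative of the two, so the sponsor should confirm it on clinical grounds.
4. **Query only:** ask the sponsor whether Table 2-5 (Grade 2 or below) or Section 7.3.2.4 (below Grade 2) governs re-start.

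The cost is a short amendment and a memo to sites, with no added patients, visits or analyses.

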7.3.2.4 Continuation of treatment with anetumab ravtansine

Treatment with anetumab ravtansine could be re-started at the appropriate dose if the TEAE requiring dose modification has resolved to Grade < 2 within 6 weeks after the last dose of anetumab ravtansine.

7.3.2.5 Permanent discontinuation of anetumab ravtansine due to TEAEs

See Section 6.3.1.2 for withdrawal criteria.

7.4 Drug logistics and accountability

All study drugs will be stored at the investigational site in accordance with GCP and GMP requirements and the instructions given by the clinical supplies department of the sponsor, and will be inaccessible to unauthorized personnel. Special storage conditions and a complete record of batch numbers and expiry dates can be found in the sponsor's study file; the site-relevant elements of this information will be available in the investigator site file. The personnel will use the study drug only within the framework of this clinical study and in accordance with this protocol. Receipt, distribution, return and destruction (if any) of the study drug must be properly documented according to the sponsor's agreed and specified procedures.

The Yale Cancer Center (YCC) will be the coordinating center for the distribution of drugs or supplies to the participating institution(s). The Investigational Drug Service (IDS) at Yale-New Haven Hospital will be employed to serve as the central pharmacy. Distribution of drugs and supplies will be conducted in adherence with the established policies of Yale-New Haven Hospital and Medical Center

The study drug will be provided by Bayer and shipped to the IDS at Yale-New Haven Hospital which will then distribute to the collaborating sites. Drug vials will be provided by Bayer with a generic non-study specific label on the cartons containing the vials. Any study specific labeling to the vials to meet local requirements will need to be done by the IDS. The vials will be distributed to collaborating sites as required by IDS.

The number of vials used will be recorded on the appropriate treatment dispensing form. Reasons for dose delay and reduction will be recorded in the source documents and on the CRF.

Treatment accountability on patient level must be verified at every cycle, starting on C1D1. The monitor will review overall drug accountability and destruction per the site documentation only.

Written instructions on medication destruction will be made available to affected parties as applicable.

7.5 Treatment compliance

The administration of anetumab ravtansine will be performed in the clinic on Day 1 of each 21-day cycle for anetumab ravtansine. Each administration must be recorded on the CRF and Drug Dispensing / Accountability Form.

Reasons for dose delay, reduction, or omission will also be recorded in the source documents and on the CRF.

An adequate record of receipt, distribution, and return of all study drugs must be kept in the form of a Drug Accountability Form.

The preparation and administration of anetumab ravtansine will be performed by members of the investigator team during hospitalization and site visits. These persons will ascertain and document that the patient receives all treatments as planned.

Patient compliance with the treatment and protocol includes willingness to comply with all aspects of the protocol, and to have blood collected for all safety evaluations. At the discretion of the principal investigator or sponsor, a patient may be discontinued from the study treatment for non-compliance with visits or study drug.

8. Non-study therapy

